8.2.4 Liver Imaging Assessments

Abdominal hepatic ultrasound will be conducted at screening and during the study as outlined in the SoA (the SoA(s) for each treatment arm is provided in the respective appendix as listed in Appendix 6) for HCC surveillance, as participants with CHB are at risk of disease progression to liver cirrhosis and/or developing HCC.

Staging of liver fibrosis will be conducted at screening in order to exclude participants with significant fibrosis/cirrhosis (Metavir F3/F4). Liver biopsy or transient elastography/ARFI/MR results obtained within 6 months prior to randomization are also acceptable. Acceptable non-invasive assessments for staging degree of fibrosis for this study includes transient elastography (Fibroscan) (Li et al 2018), acoustic radiation force impulse (ARFI) elastography (Dong et al 2015), and magnetic resonance (MR) elastography (Huwart et al 2008).

Of the above, liver stiffness measurement using transient elastography has been widely accepted in the assessment and staging of liver fibrosis. Transient elastography should be performed on a participant lying supine with the right arm elevated to facilitate access to the right liver lobe. A participant has to be in fasted state. At each assessment, at least 10 valid measurements should be taken and the following results recorded:

- No. of readings taken & reading success rate (n, %)
- Median stiffness (kPa)
- Interquartile range / IQR (kPa)
- Controlled attenuation parameter (CAP), if available

The final result of a transient electrography assessment can be regarded as valid if the number of valid readings is ≥10, the success rate (ratio of valid readings to total number

of readings) is > 60%, and the IQR (reflecting variability of measurements) is less than 30% of the median liver stiffness measurements (EASL-ALEH 2015).

8.2.5 Clinical Safety Laboratory Assessments

A list of clinical laboratory tests to be performed is provided in Appendix 4 and these assessments must be conducted in accordance with the separate laboratory manual and the SoA (the SoA(s) for each treatment arm is provided in the respective appendix as listed in Appendix 6). Normal ranges for the laboratory parameters must be supplied to the Sponsor if local laboratory is used.

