Appendix 4-Table 1 Protocol-Required Safety Laboratory Assessments

Laboratory Assessments	Parameters
Hematology	 Leucocytes, erythrocytes, hemoglobin, hematocrit, platelets, differential count (neutrophils, eosinophils, basophils, monocytes, lymphocytes), mean corpuscular hemoglobin (MCH), mean corpuscular hemoglobin concentration (MCHC) and glycated hemoglobin (HbA1c).
Clinical Chemistry	 Sodium, potassium, chloride, bicarbonate, phosphorus, calcium, magnesium, urea, uric acid, blood urea nitrogen (BUN), creatinine and cystatin C, estimated glomerular filtration rate (eGFR), glucose, total protein, albumin, total and direct bilirubin, alkaline phosphatase (ALP), ALT, AST, gamma-glutamyl transferase (GGT), alpha fetoprotein, glutamate dehydrogenase (GLDH), lipase, creatine kinase/creatine phosphokinase (CK/CPK), LDH and amylase.
Lipids	 Total cholesterol, low-density lipoproteins (LDL) cholesterol, high-density lipoproteins (HDL) cholesterol, triglycerides.
Thyroid Function Tests	 TSH, free T3 and free T4.
Coagulation	 INR, activated partial thromboplastin time, PT.
Viral Serology	 HIV (specific tests HIV-1 antibody, HIV-1/2 antibody, HIV-2 antibody), hepatitis A virus (HAV IgM antibody), hepatitis B surface antigen (HBsAg), hepatitis C virus (HCV) antibody, hepatitis D virus (HDV) antibody, hepatitis E virus (HEV) antibody.
Pregnancy Test	 All women of childbearing potential (including those who have had a tubal occlusion/ligation) will have a blood pregnancy test at screening. Urine pregnancy tests will be performed at subsequent visits according to SOAs. If a urine pregnancy test is positive, it must be confirmed by a blood pregnancy test.
Urinalysis	Specific gravity.
	 Dipstick: pH, glucose, protein, blood, ketones, bilirubin, urobilinogen, nitrites, leukocytes.
	If there is a clinically significant positive result (e.g., 2+ or greater for blood, protein or leukocytes) confirmed by a positive repeated sample, urine will be sent to the central laboratory for microscopy and culture. In addition, if there is clinically significant proteinuria (2+ or greater for protein), central laboratory will measure the urine protein: creatinine ratio.
	If there is an explanation for the positive dipstick results (e.g., menses), it should be recorded and there is no need to perform microscopy and culture.
	 Microscopic examination (sediment, red blood cells [RBCs], WBCs, casts, crystals, epithelial cells, bacteria), if blood or protein is abnormal.

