Other Screening Tests	 Alcohol and drug screen according to local procedure to include at minimum: amphetamines, barbiturates, cocaine, opiates, cannabinoids, and benzodiazepines.
	 Auto-antibodies (ANA, AMA, ASMA, a-TPO).

Investigators must document their review of each laboratory safety report.

Additional Statistical Considerations for Clinical Laboratory Data

Standard Reference Ranges and Transformation of Data

Potential analysis considerations for analyzing laboratory data includes the use of standard reference ranges and potential transformation of data for specific lab tests.

In this scenario, Roche standard reference ranges, rather than the reference ranges of the Investigator, can be used for specific parameters. For these parameters, the measured laboratory test result will be assessed directly using the Roche standard reference range. Certain laboratory parameters will be transformed to Roche's standard reference ranges.

A transformation will be performed on certain laboratory tests that lack sufficiently common procedures and have a wide range of Investigator ranges, e.g., enzyme tests that include AST, ALT, and alkaline phosphatase and total bilirubin. Since the standard reference ranges for these parameters have a lower limit of zero, only the upper limits of the ranges will be used in transforming the data.

Definition of Laboratory Abnormalities

For all laboratory parameters included in this analysis, there exists a Roche predefined standard reference range. Laboratory values falling outside this standard reference range will be labeled "H" for high or "L" for low in participant listings of laboratory data.

In addition to the standard reference range, a marked reference range has been predefined by Roche for these laboratory parameters. The marked reference range is broader than the standard reference range. Values falling outside the marked reference range that also represent a defined change from baseline will be considered marked laboratory abnormalities (i.e., potentially clinically relevant). If a baseline value is not available for a participant, the midpoint of the standard reference range will be used as the participant's baseline value for the purposes of determining marked laboratory abnormalities. Marked laboratory abnormalities will be labeled in the participant listings as "HH" for very high or "LL" for very low.

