1.1 OBJECTIVES AND ENDPOINTS

Table 1 Primary and Secondary Objectives and Corresponding Endpoints

Primary Objective(s)	Corresponding Endpoints
To estimate the effect of NME combination therapies on inducing a functional cure over the control arm.	% participants with HBsAg loss (loss (i.e., HBsAg <0.05 IU/mL) at 24 weeks post-EOT.
Secondary Objective(s) ^a	Corresponding Endpoints
To characterize the efficacy	% participants with HBsAg loss.
profile of NME combination therapies.	% participants with HBsAg seroconversion.
	 % participants with HBeAg loss (baseline HBeAg-positive participants).
	 % participants with HBeAg seroconversion (baseline HBeAg-positive participants).
	 % participants with HBV DNA < lower limit of quantification (LLOQ), <200 IU/mL and <2,000 IU/mL.
 To characterize the PD profile of NME combination therapies. 	 Change from baseline in quantitative HBsAg, anti-HBs, HBeAg, anti-HBe, HBcrAg, HBV RNA, and HBV DNA levels over time.
To characterize the plasma PK profiles of NMEs.	Estimated PK parameters from sparse sampling and population PK models (included below parameters but not limited to)
	Area under the curve (AUC)
	Peak Concentration (Cmax)
	Volume of distribution (Vd)
	Clearance (CL)

		Urir	ne PK
•	To assess the safety and tolerability of NME combination therapies.	•	Incidence, nature and severity of adverse events.
		•	Incidence of laboratory abnormalities based on hematology, clinical chemistry, lipids, thyroid function tests, coagulation, urinalysis test.
		•	ECGs.
		•	Vital signs including blood pressure, pulse rate, respiratory rate and body temperature.
		•	Anti-drug antibodies (ADA) (if applicable)
•	To identify presence of PK/PD relationship.	•	Analyses of PK/PD data.
•	To explore potential effects of ADA on NMEs and/or IMP, as applicable.	•	Relationship between ADA status, PK, safety, PD, and efficacy.
	Exploratory Objective(s)		Corresponding Endpoints
•	To characterize the profile of novel viral response markers.	•	Profiles and changes from baseline of total HBsAg post-dissociation of HBsAg-HBsAb complexes/components of HBsAg and quantitative anti-HBc (IgG or total).
•	To assess the relationship between baseline disease characteristics and efficacy/safety responses.	•	Association between primary and secondary outcomes and HBV genotype (obtained using HBV RNA or DNA sequencing and/or any alternative methodology, and/or from medical records prior to study entry).

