4.5.3.1 Laboratory Data

All laboratory data will be reported in terms of standard ranges in System international (SI) units and will be converted from the original units as necessary.

Summary tables will detail the transformed values and change from baseline of the laboratory parameters over time by treatment group.

Absolute values and changes from baseline over time plots will be provided.

Data processing rules-

Combination Therapies for CHB—F. Hoffmann-La Roche Ltd Statistical Analysis Plan WV41073

- Unscheduled visit: If more than one visit occurred during a single visit window, then the laboratory data closest to the scheduled visit day will be used. If the two laboratory assessments were equidistant from the scheduled visit day, then the later assessment will be used.
 - All unscheduled labs will be included in lab profile plots over time, and also listed by day relative to start of treatment including the clinical planned event CPE (visit) listed also.
- 2) Baseline visit: If the baseline value is missing, value from closest screening visit will be used. If two or more samples were collected on the day that was closest to the Baseline target day, then the earliest sample was selected; if the sample collection time was the same then the worst value was selected.
- Values below limit of quantification will be set to limit of quantification.
- 4) Local laboratory results may be available. If both local and central laboratory results are available for same time point, then central lab results should be used for analyses. In cases where only the local laboratory results exist for a given timepoint, these will be normalized using the Roche document for analysis Data Analysis Guidance: Safety Lab standardization (Please refer the output specification).

Laboratory Abnormalities:

Division of AIDS (DAIDS) Table for Grading the Severity of Adult and Pediatric Adverse Events AE grading will be used to present shifts from baseline to the worst grade observed during treatment. For protocol-required safety laboratory assessments, please refer to protocol Appendix 4- Table 1.

Shift tables will provide shifts from DAIDS grade at baseline to DAIDS grade on treatment, where baseline is defined as the last valid, non-missing assessment prior to the first study drug administration, and percentages are based on the number of participants with valid measurement at baseline.

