4.6 OTHER ANALYSES

4.6.1 Summaries of Conduct of Study

The number of participants who were randomized, discontinued treatment, completed treatment, discontinued study and completed the study (including follow-up period) will be summarized by treatment. Major protocol deviations will be summarized and listed by each treatment arm. Separate listing will be provided for the patients who have met the NUC discontinuation criteria at EOT or follow-up but have not stopped NUC (reluctant to do).

For each participant assessment, the baseline value will be the latest non-missing assessment prior to the first dose administration, this being study Day 1 pre-dose. In the absence of data on study Day 1, the latest non-missing value collected during screening will be used, if such data are not available then the assessment baseline value will be missing for that participant.

4.6.2 Summaries of Treatment Group Comparability/Demographics and Baseline Characteristics

Descriptive statistics will be generated for demographic and baseline disease characteristics including sex, race, ethnicity, origin (for Asian participants only), age, weight, height, body mass index, HBV DNA and HBsAg levels, and HBV history including but not limited to duration of HBV disease, likely route of transmission, HBV genotype, HBeAg status, previous HBV treatments (including incidence of Peg-IFN), and length of time on NUCs.

For NUC treatment duration calculation, if there is a break of treatment of less than 6 months then the duration will be cumulative, if break of treatment is more than 6 months, then the last continuous course of treatment with any nucleos(t)ide products prior to baseline (categorized as <3 years, >=3 to <5 years, >=5 years to <10 years, and >=10 years) will be counted. The effect of this duration covariate will be examined with respect to efficacy, immunogenicity, and antiviral endpoints in separate analyses.

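### The 36-week PD-L1 schedule has no end-of-treatment alpha-fetoprotein mark, unlike every other treatment-period schedule (minor; with a query on lipid timing)

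*Protocol*

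**What the plan says.** **Alpha-fetoprotein.** Every schedule of activities gives alpha-fetoprotein its own row. In Appendix 13-Table 8 that row has one mark, in the screening column. In the same table the abdominal ultrasound row is marked at screening and Week 37, thyroid tests at screening, Week 25 and Week 37, and Chemistry at every treatment-period visit. Appendix 13-Table 9 (follow-up for both PD-L1 arms) marks alpha-fetoprotein at follow-up Weeks 24 and 48.

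Appendix 4-Table 1 also names the analyte within the Clinical Chemistry panel: "gamma-glutamyl transferase (GGT), alpha fetoprotein, glutamate dehydrogenase (GLDH), lipase". Protocol 8.2 refers the reader to the schedule for the planned times of all safety assessments, and 8.11.2 requires assessments to follow it. Section 8.2.4 describes ultrasound as being done "for HCC surveillance, as participants with CHB are at risk of disease progression to liver cirrhosis and/or developing HCC".

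**Lipids.** Appendix 4-Table 1 has a lipid panel, separate from Clinical Chemistry: "Total cholesterol, low-density lipoproteins (LDL) cholesterol, high-density lipoproteins (HDL) cholesterol, triglycerides". SAP Table 1 defines the endpoint as "Incidence of laboratory abnormalities based on hematology, clinical chemistry, lipids, thyroid function tests, coagulation, urinalysis test", and SAP 4.5.3.1 adds: "For protocol-required safety laboratory assessments, please refer to protocol Appendix 4- Table 1". On timing, Protocol 8.2.5 says that "these assessments must be conducted in accordance with the separate laboratory manual and the SoA".

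**The concern.** In the other seven treatment-period schedules, alpha-fetoprotein and ultrasound are both marked at end of treatment. Only Table 8 separates them, and no reason is given. Exclusion criterion 4 uses a raised alpha-fetoprotein as its leading example of suspected hepatocellular carcinoma, so the protocol itself treats the marker as informative. A site that follows the table would not draw it at Week 37, and arm 9 would lack the end-of-treatment value that the other arms have. What is at stake is one safety marker in one arm of about 30 participants.

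The lipid item is of a different kind. A panel is named as required and counted in a descriptive safety endpoint, yet the protocol does not say when to draw it.

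**Working it through.** The plan gives no figure to reproduce here. The check compares tables and adds some calendar arithmetic.

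**Step 1. Alpha-fetoprotein marks in the eight treatment-period schedules**

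| Schedule | Arm | Marks up to end of treatment |
|---|---|---|
| Appendix 7-Table 2 | NUC control | Screening, Week 24, Week 48 (end) |
| Appendix 8-Table 4 | CpAM + TLR7 | Screening, Week 25, Week 48 (end) |
| Appendix 9-Table 3 | siRNA | Screening, Week 25, Week 49 (end) |
| Appendix 10-Table 3 | siRNA + PEG-IFN | Screening, Week 25, Week 49 (end) |
| Appendix 11-Table 3 | siRNA + CpAM | Screening, Week 25, Week 49 (end) |
| Appendix 12-Table 4 | siRNA + TLR7 | Screening, Week 25, Week 49 (end) |
| Appendix 13-Table 7 | PD-L1, 24 weeks | Screening, Week 25 (end) |
| Appendix 13-Table 8 | PD-L1, 36 weeks | Screening only |

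An end-of-treatment mark is present in 7 of 8.

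**Step 2. Which part of the protocol sets timing.** Sections 8.2 and 8.11.2 give timing to the schedule; Appendix 4 lists what is measured. Two parallels support this reading.
- HbA1c is listed within Hematology in Appendix 4, but schedule footnotes limit it to screening.
- GLDH is listed within Clinical Chemistry, but it has its own row, and the unscheduled-visit list in 8.3.8.2 names it beside chemistry.

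A separate alpha-fetoprotein row would serve no purpose if the test ran with every Chemistry draw. The row therefore governs.

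**Step 3. Consequence for arm 9.** Inputs: Week 37 is Day 253 (Table 8); follow-up Week 24 is Day 168 of follow-up (Table 9), counted from the Week 37 visit.
- With a Week 37 mark, the first repeat is (253 − 1)/7 = 252/7 = 36 weeks after Day 1.
- As written, it is (252 + 168)/7 = 420/7 = 60 weeks after Day 1.
- Delay: 60 − 36 = 24 weeks.
- The screening window runs from Day −56 to Day −7, that is 8 to 1 weeks before Day 1. Measured from screening, the first repeat is at 61 to 68 weeks instead of 37 to 44.
- If the 6-week extension that Table 9 allows in extreme circumstances is used, 60 becomes 60 + 6 = 66 weeks.

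For comparison, the first repeat elsewhere is at Day 169, (169 − 1)/7 = 24 weeks after Day 1, or at Day 168 in the control arm, 167/7 = 23.9 weeks.

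**Step 4. Lipids.** Fifteen schedules were read: the eight above, plus Appendix 6-Table 4, 8-Table 5, 9-Table 4, 10-Table 4, 11-Table 4, 12-Table 5 and 13-Table 9. Lipid rows: 0. Footnotes placing lipids under Chemistry: 0. Lipids are 1 of the 6 panels in the SAP endpoint.

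**The case against.** **The mark may have been lost when the table was read from PDF.** This cannot be excluded. Against it, the ultrasound, thyroid, Chemistry and alcohol/drug-screen rows of the same table keep their Week 37 marks. The objection stands as a reason to check the source table before changing anything.

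**The practical effect is small.** This stands. Ultrasound, the test that 8.2.4 ties to liver-cancer surveillance, is still done at Week 37. Alpha-fetoprotein is measured at follow-up Weeks 24 and 48, and Appendix 4 lets the investigator add tests at any time. A reader might infer that arm 9 has no liver-cancer surveillance at end of treatment; the ultrasound mark rules that out.

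**Appendix 4 puts alpha-fetoprotein in Clinical Chemistry, so it is drawn anyway.** A reader might go further and infer an unresolved conflict: no treatment-period tests by the row, 19 by the panel. The documents do not support that, because 8.2 and 8.11.2 assign timing to the schedule. The overlap is not peculiar to arm 9 either: every treatment-period schedule has an alpha-fetoprotein row sparser than Chemistry. What is peculiar to Table 8 is the missing end-of-treatment mark.

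**The lipid item depends on a document that is not supplied.** This stands, and it is why lipids are only a query. Section 8.2.5 relies on the laboratory manual as well as the schedule, and schedule rows do not match Appendix 4 panels one to one. A reader might infer that lipids are never collected and that one endpoint component has no data; a missing row does not show that.

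A reader might also link two baseline rules. SAP 4.6.1 says "if such data are not available then the assessment baseline value will be missing for that participant", while Appendix 4 says "If a baseline value is not available for a participant, the midpoint of the standard reference range will be used". From these one could argue that lipid abnormalities would be judged against an invented baseline. That is not supported. SAP 4.1 allows repeat and unscheduled pre-dose values to serve as baseline, and the midpoint rule applies only to the marked-abnormality flag.

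**Conclusion.** The alpha-fetoprotein point holds as a minor safety-schedule correction. As written, arm 9 has no end-of-treatment test, and its first repeat comes 24 weeks later than a Week 37 mark would give. About 30 participants are concerned, with up to about 30 more if the additional recruitment in Protocol 9.2 is used. There is no effect on the primary endpoint, on power or on any efficacy analysis.

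The conclusion rests on two assumptions: that the blank cell is in the source table, and that sites follow the schedule row, as 8.2 and 8.11.2 direct. No reason for treating arm 9 differently is given, so an oversight is more likely than a choice.

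For lipids, the documents show only that no schedule states a draw time. Whether anything is missing depends on the laboratory manual. No arm appendix names a lipid risk, and the endpoint is descriptive.

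**What to change.** **Alpha-fetoprotein.** Check the row in the source of Appendix 13-Table 8. If the Week 37 cell is blank there, add the mark at Week 37 (Day 253). Blood is already drawn and ultrasound repeated at that visit, so the cost is one extra assay per participant, about 30 in all at the planned size, with no new visit. Arm 9 is planned in the protocol and ongoing in the SAP, so the change helps only participants who have not yet passed Week 37.

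**Lipids (query).** Look in the laboratory manual. If lipids run with Chemistry, add a footnote to the Chemistry rows saying so, as is already done for HbA1c under Hematology. If they do not, delete the panel from Appendix 4-Table 1 and the word from SAP Table 1. Either way the cost is editorial.

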Appendix 5 Contraceptive Guidance and Collection of Pregnancy Information

1. **DEFINITIONS**

Woman of Childbearing Potential (WOCBP)

A woman is considered fertile following menarche and until becoming post-menopausal unless permanently sterile. The definition of childbearing potential may be adapted for alignment with local guidelines or requirements.

- Women in the following categories are considered to be Woman of Non-Childbearing Potential (WONCBP)
- a) Pre-menarchal
- b) Pre-menopausal female with one of the following:
 - Documented hysterectomy.
 - Documented bilateral salpingectomy.
 - Documented bilateral oophorectomy.

Note: Documentation can come from the site personnel's: review of participant's medical records, medical examination, or medical history interview.

c) Post-menopausal female

- A post-menopausal state is defined as no menses for ≥ 12 months without an alternative medical cause other than menopause. A high follicle-stimulating hormone (FSH) level in the post-menopausal range may be used to confirm a post-menopausal state in women not using hormonal contraception or hormonal replacement therapy (HRT). However, in the absence of 12 months of amenorrhea, a single FSH measurement is insufficient.
- Females on HRT and whose menopausal status is in doubt will be required to use one of the non-hormonal highly effective contraception methods if they wish to continue their HRT during the study. Otherwise, they must discontinue HRT to allow confirmation of post-menopausal status before study enrollment.

2. CONTRACEPTION GUIDANCE

Female Participants

Unless otherwise stated in the respective appendix of each treatment arm, female participants of childbearing potential are eligible to participate if they agree to use highly

effective method of contraception consistently and correctly as described in Appendix 5-Table 1 below.

Per ICH M3 (R2), highly effective methods of birth control are defined as those, alone or in combination, that result in a low failure rate (i.e. less than 1% per year) when used consistently and correctly as described in Appendix 5-Table 1 below.

